7 INVESTIGATIONAL PLAN

This study is a multicenter clinical trial and is designed as a proof-of-concept study to evaluate the efficacy, safety, tolerability, PK, immunogenicity, and PD/biomarker of BSI-045B following SC injections.

The present study, which is intended to assess the efficacy and safety of BSI-045B in moderate to severe AD patients, is being conducted as a proof-of-concept study prior to performing a more traditional Phase 2 trial. If this study is successful, the Sponsor plans to conduct a future Phase 2b, randomized, blinded, dose-finding trial that will formally compare BSI-045B with placebo and/or other treatments for AD.

7.1 Study Dosing

The total number of evaluable patients with AD will be approximately 20 to 24.

Patients will initially be treated with a loading dose of BSI-045B given QW for 4 weeks. Thereafter, BSI-045B will be given at Q2W interval to Week 24.

7.2 Washout Period

Patients will start with a washout period for anti-AD treatment prior to study treatment, including systemic and topical agents and phototherapy. The duration of the washout period varies by therapy and the Investigator should consult Table 6. Eligible patients who complete the washout period for previous therapies for AD will be treated with BSI-045B.

Washout period is required for patients already on treatment for AD. Washout duration requirements is described in Table 6.

Table 6. Washout Durations Required Before Initial Dose of BSI-045B, by Therapy

Therapy	Washout Duration Required before First Dose of BSI-045B
Tralokinumab	12 weeks
Dupilumab	12 weeks
Phototherapy	4 weeks
Abrocitinib	4 weeks
Upadacitinib	4 weeks
Topical corticosteroids	1 week
Topical calcineurin inhibitors	1 week
Investigational Products	4 weeks
All Other Therapies prescribed for therapeutic	3 weeks or 4 half-lives, whichever is
immunosuppression or immunomodulation	longer

7.3 Replacement of Patients who Withdraw from Treatment

Patients who do not complete the first 5 doses of BSI-045B will be replaced.

V4.0_8 Jul 2024 Page 40 of 68

7.4 Monitoring by Safety Steering Committee

The Safety Steering Committee (SSC) will monitor the study and will be composed of representatives from the Sponsor, the National Principal Investigator, and independent physicians, as indicated in the SSC charter.

The SSC will formally assess safety findings when 20 patients complete dosing at Week 12. The SSC will assess all events, especially treatment-related serious adverse events (SAEs) that might prompt a change to the study.

7.5 Assessment of Primary Efficacy Endpoint

The primary efficacy endpoint is the proportion of patients with ≥EASI75 at Week 26 (2 weeks after last dose at Week 24), compared with baseline (Day 1).

7.6 Other Efficacy and Safety Assessments

Additional efficacy outcomes will include other scores on EASI, Investigator's Global Assessment (IGA), Facial IGA, assessment of conjunctivitis, and Peak Pruritus Numerical Rating Scale (PP-NRS). Efficacy assessments will be conducted prior to dosing on Day 1, at all subsequent visits, and at the time of early withdrawal from the study.

Adverse events (AEs) will be collected after signing the ICF and throughout the Treatment Period and the Follow-Up Period. After injections, all patients should be monitored at the study sites for at least 30 mins to observe body reactions, including injection site reactions. Any injection site reactions observed after each site visit should be reported to the Investigators by the patients.

Concomitant medications will be recorded after signing the ICF and throughout the Treatment Period and Follow-Up Period.

During the Treatment and Follow-up Periods, PK and PD samples will be collected for analysis. Immunogenicity will be assessed throughout the Treatment Period and Follow-up Period.

Follow-up assessments will occur during subsequent visits to the study sites. At the Investigator's discretion, patients may return to the study sites at other times for reevaluation.

7.7 Follow-up Period

After the Treatment Period, there will be a 12-week Follow-up Period.

7.8 Study Drug Administration

The preferred SC injection site is the abdomen. The thigh can be used as an alternative site for SC injections. A 2.5 mL injection of 120 mg/mL (300 mg total dose) will be administered at a single injection site.

V4.0_8 Jul 2024 Page 41 of 68

7.9 Enrollment and Study Procedures

7.9.1 General Considerations

Patients will be assigned a screening identification number once they have signed the ICF and will then be considered enrolled into the study if they have been determined to satisfy all inclusion and exclusion criteria (and after washout if requiring washout).

When collecting PK samples, immunogenicity, PD/biomarker, and clinical laboratory samples, vital signs, and/or ECG assessments are scheduled to occur at the same time point, ECG and vital signs testing will be performed prior to blood collections. The preferred order of assessments is:

- 1) ECG
- 2) Vital signs
- 3) PK, Immunogenicity, PD/biomarker sampling
- 4) Clinical laboratory sampling

Samples for serum PK (collected at nominal times), ADA, and PD/biomarker assessments will be collected for PK and ADA assessments using GLP validated assays and for PD/biomarker assessments using fit-for-purpose, qualified assays with commercial kits. Refer to the laboratory manual for additional details on laboratory assessment and sample processing.

7.9.2 Assessments at Screening

Screening assessments will be performed after the patients signed the ICF. After all screening results are obtained, eligible patients who require no washout will be enrolled to the study directly; eligible patients who require washout will start washout and repeat some screening assessments during Day-14 to Day-1.

Rescreening is allowed after a delay of at least 4 weeks from the initial screening assessment. Any rescreening should be approved by the Sponsor.

A complete history will be recorded at Screening and will include medical history, surgical history, smoking history, alcohol use history, drug abuse history, prior and current medication, blood donation history, allergy history, and other demographic information.

Physical examinations at Screening will include weight, height, and body mass index (BMI), as well as a complete examination. Symptom-driven examinations will be performed at other time points.

Other screening assessments will include 12-lead ECG, blood pregnancy test (females of childbearing potential only), and vital signs (blood pressure, pulse, temperature, and

V4.0_8 Jul 2024 Page 42 of 68

respiratory rate). A subset of these tests will be completed at other time points, as detailed in the Schedule of Activities.

A screening for drugs of abuse is optional (per the discretion of the Investigator).

Clinical laboratory assessments at Screening will include those listed in Table 7 and will be conducted as site policy requires.

Table 7. Clinical Laboratory Assessments, BSI-045B-002

Type of Test	Laboratory Parameters
Hematology	Hemoglobin, hematocrit, WBC count and differential, RBC count and indices, platelet count
Chemistry	Sodium, potassium, chloride, bicarbonate, calcium, phosphorus, magnesium, glucose, BUN, creatinine, uric acid, ALT, AST, GGT, alkaline phosphatase, total protein, albumin, globulin, total bilirubin, LDH, total cholesterol, triglycerides
Coagulation	PT, aPTT, fibrinogen, INR
Virology (performed only at Screening)	HbsAg, anti-HCV, HIV
Urinalysis	Protein, glucose, ketones, occult blood, urobilinogen, urine sediment microscopy (if other parameters abnormal)

ALT = alanine aminotransferase; aPTT = activated partial thromboplastin time; AST = aspartate aminotransferase; DNA = deoxyribonucleic acid; ECG = electrocardiography; GGT = gamma glutamyl transferase; HbsAg = hepatitis B surface antigen; HBV = hepatitis B virus; HCV = hepatitis C virus; HIV = human immunodeficiency virus; INR = international normalized ratio; LDH = lactate dehydrogenase; PCR = polymerase chain reaction; PT = prothrombin time; RBC = red blood cell; WBC = white blood cell

7.9.3 Efficacy

Patients will be assessed to determine an EASI score at Screening, prior to dosing on Day 1 (baseline), at subsequent visits, and at the time of early withdrawal from the study.

The EASI score is a composite index that measures the severity of AD based on the average intensity of four clinical signs (erythema, edema/papulation, excoriations, and lichenification) at four body areas (head, neck, upper extremities, and trunk and lower extremities), and the percentage of affected area for each of the four body areas (Hanifin and Rajka, 1980). The primary efficacy endpoint is the proportion of patients with ≥EASI75 at Week 26 (2 weeks after last dose at Week 24).

The IGA and facial IGA require the Investigator to rate the severity of AD on a scale from 0 (clear) to 4 (severe).

The assessment tool for itching is the PP-NRS, on which the patient rates the maximum severity of the itch from AD on a scale from 0 (no itch) to 10 (worst itch imaginable) over a

V4.0_8 Jul 2024 Page 43 of 68

24-hour period. The baseline PP-NRS score is based on the average of daily PP-NRS scores for the 7 days immediately preceding Day 1. Patients will complete the rating scale daily using the patient diary beginning on Day -8, throughout the last study visit, and at the time of early withdrawal from the study. In order to calculate an average for the score, the patient must have completed the diary for a minimum of 4 days during the previous 7 days.

Exploratory efficacy and safety assessments will include the following. At each visit, the percentage of patients who achieve 50%, 75%, and 90% improvement in the EASI score from Day 1) and the change in EASI score from Day 1 will be calculated. Detailed analysis of all exploratory endpoint is described in the Statistical Analysis Plan (SAP).

- Proportion of patients with EASI90 at Week 26 (2 weeks after last dose at Week 24)
- Proportion of patients with EASI50 at Week 26 (2 weeks after last dose at Week 24)
- Percent change from baseline in EASI at each visit
- Proportion of patients achieving IGA 0 or 1 Week 26 (2 weeks after last dose at Week 24)
- Percent changes in PP-NRS scores at Week 26 (2 weeks after last dose at Week 24)
- Proportion of patients achieving Facial IGA 0/1 at Week 26 (2 weeks after last dose at Week 24)
- Occurrence of conjunctivitis

7.9.4 *Safety*

The safety of BSI-045B will be assessed by the incidence of AEs, anti-BSI-045B ADA formation, clinical laboratory evaluations, 12-lead ECGs, vital signs, physical examinations, occurrence of conjunctivitis, as well as injection site reactions. The relationships between study medication and AEs will be evaluated by the Investigators.

Assessments will occur during visits to the study sites or via videoconference or telephone conference. Adverse events will be collected throughout the Treatment Period and the Follow-Up Period to determine whether there are ongoing AEs, SAEs, worsening of AEs or SAEs, or development of new AEs or SAEs. Follow-up of AEs and SAEs will occur during clinic visits and whenever abnormal, clinically significant findings are observed. Concomitant medications taken after the final dose of BSI-045B will be recorded throughout the Follow-Up Period. At the Investigator's discretion, patients may be brought back to the study sites at other times for re-evaluation.

For the assessment of conjunctivitis, conjunctivitis history will be asked at screening visit, and all patients will be asked if they had been diagnosed as conjunctivitis at every visit during study treatment period. For patients who have been diagnosed as conjunctivitis, the conjunctivitis severity will be asked, and the severity grades include: 0 = no conjunctivitis; 1

V4.0_8 Jul 2024 Page 44 of 68

= mild conjunctivitis; 2 = moderate conjunctivitis requiring treatment; 3 = severe conjunctivitis that may require an ophthalmic exam. Investigators should also check the patients' eyes and record any findings.

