3 SCHEDULE OF ACTIVITIES

The Schedule of Activities is divided into two tables:

Table 1. Screening and Treatment

Table 2. Follow-up, End of Study, and Early Withdrawal

Table 1. Screening and Treatment

		Treatment Period															
Study Procedure	Screening	QW Loading Dose															T
	1	W1		W1	W2	W3	W4	W6	W8	W10	W12	W14	W16	W18	W20	W22	
		Predosing ²	Dosing and after	D2	(±1d)	(±1d)	(±3d)										
Sign ICF	X																
Inclusion/exclusion criteria	X	X															
Medical history, demographics	X																
Assessment of suicidality (PH-2)	X																
AD medication washout	X																
BSI-045B administration			X		X	X						X^3					
12-lead ECG ⁴	X	X		X	X		X		X		X			X		X	X
Vital signs ⁴	X	X		X	X		X		X		X		X		X		X
Physical examination ⁵	X	X		X	X		X		X		X		X		X		X
Clinical labs ^{4,6}	X^7	X			X		X		X		X		X		X		X
Blood pregnancy test (females of childbearing potential only)	X																
Urine pregnancy testing (females of childbearing potential only)		X					X		X		X		X		X		X
Urine toxicology for drugs of abuse (optional) ⁸	X^7																
Virology screen ^{4,8}	X																
Assess for injection site reaction ¹⁰			X	X							X						

V4.0_8 Jul 2024 Page 17 of 68

								Treati	ment P	eriod							
	Screening	QW Loading Dose															
Study Procedure	1	W1	W1 D1		W2	W3	W4	W6	W8	W10	W12	W14	W16	W18	W20	W22	1 1
		Predosing ²	Dosing and after	D2	(±1d)	(±1d)	(±3d)	(±3d)	(±3d)	(±3d)	(±3d)	(±3d)	(±3d)	(±3d)	(±3d)	(±3d)	(±3d)
Efficacy and safety assessments and patient diary (EASI, IGA, facial IGA, PP- NRS, assessment of conjunctivitis) ¹¹	X	X			X	X	X	X	X	X	X	X	X	X	X	X	X
PK sample collection ^{4,11}		X			X	X	X	X	X	X	X	X	X	X	X	X	X
Immunogenicity sample collection ^{4,13}		X			X	X	X		X		X		X		X		X
PD Biomarker sample collection ^{4,14}		X			X	X	X		X		X		X		X		X
Assess concomitant medications								X									
Monitor and document AEs				•		•	•	X					•	•		•	

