- 6. Clinical laboratory assessments:
- Hematology: Hemoglobin, hematocrit, WBC count and differential, RBC count and indices, platelet count
- *Chemistry*: Sodium, potassium, chloride, bicarbonate, calcium, phosphorus, magnesium, glucose, BUN, creatinine, uric acid, ALT, AST, GGT, alkaline phosphatase, total protein, albumin, globulin, total bilirubin, LDH, total cholesterol, triglycerides
- Coagulation: PT, aPTT, fibrinogen, INR
- *Urinalysis*: Protein, glucose, ketones, occult blood, urobilinogen, urine sediment microscopy (if other parameters abnormal)
- 7. For patients requiring washout, clinical laboratory assessments and urine toxicology test should be repeated to make sure the tests are conducted within 14 days prior to W1D1.
- 8. Urine toxicology: Urine toxicology testing is optional. If the PI has no concerns about the use of illicit drugs by a patient, testing for drugs of abuse is not required. If the PI has concerns, a negative urine/blood result for drugs of abuse is required at Screening. Screening assessment on urine toxicology should be repeated if they are performed ≥14 days before W1D1.
- 9. Virology screening: HbsAg, anti-HCV, HIV.
- 10. All patients should be monitored in the study sites for at least 30 mins after each dose to observe body reactions, including injection site reactions. Any injection site reactions observed after each site visit should be reported to the Investigators by the patients.
- 11. Efficacy assessments: EASI, IGA, facial IGA and PP-NRS. For PP-NRS: Patients will complete the PP-NRS daily in a patient diary beginning on Day -8, throughout the last study visit, and at the time of early withdrawal from the study, and scores for each timepoint will be the average of scores over the past 7 days. In order to calculate an average for the score, the patient must have completed the diary for a minimum of 4 days during the previous 7 days. Investigator should also assess Facial IGA. For the assessment of conjunctivitis, diagnosis history with severity will be recorded at screening, and at every visit during the treatment period, all patients will be asked if they had been diagnosed as conjunctivitis since last visit. Conjunctivitis severity grade includes: 0 = no conjunctivitis; 1 = mild conjunctivitis; 2 = moderate conjunctivitis requiring treatment; 3 = severe conjunctivitis that may require an ophthalmic exam. Investigators should also check the patients' eyes and record any findings.

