- 12. PK blood sample collection: Within 1 h before each dose during the Treatment Period.
- 13. Immunogenicity blood sampling: Blood samples are to be collected at W1D1, W2, W3, W4, W8, W12, W16, W20, and W24 within 1 h before each dose during the Treatment Period.
- 14. Biomarker blood sample collection: Assessments are TARC/CCL-17, periostin, and IgE. Samples are to be obtained at W1D1, W2, W3, W4, W8, W12, W16, W20, and W24 within 1 h before each dose during the Treatment Period.

V4.0_8 Jul 2024 Page 19 of 68

Table 2. Follow-up, End of Study, and Early Withdrawal

	Follow-up Period						
Study Procedure	FU1 (2 weeks after last dose±3d)	FU2 (4 weeks after last dose±3d)	FU3 (6 weeks after last dose±3d)	FU4 (8 weeks after last dose±3d)	FU5 (10 weeks after last dose±3d)	FU6 (12 weeks after last dose±3d)	(+7d)
12-lead ECG ²	X						X
Vital signs ²	X	X	X	X	X	X	X
Physical examination (system driven)		X		X		X	X
Clinical labs ^{2,3}		X		X		X	X
Blood pregnancy test (females of childbearing potential only)							X
Urine pregnancy testing (females of childbearing potential only)		X		X		X	
Efficacy assessments and patient diary (EASI, IGA, facial IGA, PP-NRS) ⁴	X	X	X	X	X	X	X
PK sample collection ^{2,5}	X	X	X	X	X	X	X
Immunogenicity sample collection ^{2,6}		X		X		X	X
PD Biomarker sample collection ^{2,7}		X		X		X	X
Assess concomitant medications	X						
Monitor and document AEs							

AE = adverse event; ALT = alanine aminotransferase; aPTT = activated partial thromboplastin time; AST = aspartate aminotransferase; CCL-17 = C-C chemokine ligand 17; EASI = Eczema and Severity Index; ECG = electrocardiography; GGT = gamma glutamyl transferase; IGA = Investigator's Global Assessment; IgE = immunoglobulin E; IL = interleukin; INR = international normalized ratio; LDH = lactate dehydrogenase; PD = pharmacodynamic; PK = pharmacokinetic; PP-NRS = Peak Pruritus Numerical Rating Scale; PT = prothrombin time; RBC = red blood cell; TARC = thymus and activation regulated chemokine; W = week; WBC = white blood cell

- 1. Early withdrawal: Early withdrawal assessments must be completed within 7 days after the last treatment with BSI-045B or within 7 days after the patient's decision to discontinue study treatment, whichever occurs first. When medically feasible, the Medical Monitor should be consulted prior to study drug discontinuation.

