# 4.8.9 Conjunctivitis Assessment

Treatment-emergent conjunctivitis is defined as conjunctivitis that started or worsened in severity on or after the first dose of study drug.

Treatment-emergent conjunctivitis will be summarized by worst post-baseline severity score.

A listing of conjunctivitis assessment will be provided by subject number.

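### The solicited, 0-3 graded conjunctivitis assessment ends at Week 24, but the SAP table built on it has no end date (minor)

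*Protocol*

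**What the plan says.** **Collection during treatment.** Protocol Section 7.9.4 states that "all patients will be asked if they had been diagnosed as conjunctivitis at every visit during study treatment period". Footnote 11 to Table 1 agrees and adds the recall period: "at every visit during the treatment period, all patients will be asked if they had been diagnosed as conjunctivitis since last visit". Both give a severity scale from 0 (none) to 3 (severe). The Table 1 row names the item ("NRS, assessment of conjunctivitis") and is marked through the last treatment visit, Week 24.

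**Collection afterwards.** Table 2 covers FU1-FU6 (2 to 12 weeks after the last dose) and early withdrawal. Its matching row reads "Efficacy assessments and patient diary (EASI, IGA, facial IGA, PP-NRS" and does not include conjunctivitis.

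**Section 7.6.** This section lists conjunctivitis among the additional efficacy outcomes ("Facial IGA, assessment of conjunctivitis, and Peak Pruritus Numerical Rating Scale (PP-NRS"). Its next sentence says "Efficacy assessments will be conducted prior to dosing on Day 1, at all subsequent visits, and at the time of early withdrawal".

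**Analysis.** Protocol Table 5 lists the occurrence of conjunctivitis as an exploratory endpoint and gives no time window. SAP 4.8.9 says: "Treatment-emergent conjunctivitis is defined as conjunctivitis that started or worsened in severity on or after the first dose of study drug". It then summarises these cases by the worst severity score after baseline.

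**The concern.** The definition in SAP 4.8.9 is open-ended, but the data behind its table are not. The 0-3 score is defined only within the dedicated assessment, while adverse events are graded by CTCAE v5. SAP 4.8.9 does not say whether a case recorded only as an adverse event counts, or where it would appear. A reader of the table would take it to cover the whole study. For completers it would cover the time to Week 24, and for early stoppers only the time to their last treatment visit.

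The missing period is not free of drug, and conjunctivitis is one of the toxicities listed in Protocol Table 8. At stake is a graded incidence that is somewhat too low, in a study whose findings are meant to inform the design of Phase 2b. The primary efficacy analysis is not touched.

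**Working it through.** **1. Dosing grid.** Table 1 has dosing visits at Weeks 1, 2, 3, 4, 6, 8, ..., 24, which is 4 + 10 = 14 doses. 14 × 300 mg = 4200 mg, the planned total in SAP 4.8.1. The last dose is therefore at Week 24, (24 − 1) × 7 = 161 days after the first.

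**2. Coverage for a completer.** FU6 is 84 days after the last dose, so it falls 161 + 84 = 245 days (35 weeks) after the first dose.
- Days with no solicited assessment: 84/245 = 34%.
- Scheduled visits after Day 1, not counting Week 1 Day 2: 13 in treatment and 6 in follow-up. Visits without the question: 6/19 = 32%.
- SAP 4.8.1 credits 14 days of exposure to the last injection, so total exposure is (161 + 14)/7 = 25 weeks. The last 2 of these 25 weeks (8%) follow the final conjunctivitis question.

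**3. Coverage for an early stopper.** Protocol Section 7.11 asks for follow-up assessments after discontinuation. For efficacy endpoints, SAP 4.1.4 maps a patient last dosed at Week 14 to follow-up visits at Weeks 16 to 26. If that patient follows Table 2, the question covers 14 − 1 = 13 of 26 − 1 = 25 weeks. For a patient last dosed at Week 6 it covers 5 of 5 + 12 = 17 weeks. Neither patient is asked at the early withdrawal visit.

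**4. Drug remaining.** Fraction remaining = 0.5^(t / half-life), with mono-exponential decline as described in Section 5.2.3.3. The protocol's overall half-life is about 25 days (Section 5.2.3.4). The range runs from 18 days, implied by equating 90 days with about 5 half-lives in Section 8.1 (90/5), to 29.5 days, the highest single-dose mean.

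| Half-life (days) | 2 weeks after last dose | 12 weeks after last dose |
|---|---|---|
| 18 | 58% | 3.9% |
| 25 | 68% | 9.7% |
| 29.5 | 72% | 13.9% |

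At 25 days, the mean over the 12 weeks is about 39%.

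**5. Possible effect on the reported incidence.** The documents give no conjunctivitis rate, so the true incidence p by FU6 is an assumption, taken from 5% to 20%. With a constant hazard, h = −ln(1 − p)/245 per day, and the incidence seen by Week 24 is 1 − exp(−161h).

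| Assumed incidence by FU6 | Seen by Week 24 | Patients missed, n = 20 to 24 |
|---|---|---|
| 5% | 3.3% | 0.3 to 0.4 |
| 10% | 6.7% | 0.7 to 0.8 |
| 20% | 13.6% | 1.3 to 1.5 |

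If the hazard is instead constant on treatment and then falls with drug level, follow-up counts as about 84 × 0.39 = 32.6 treatment-equivalent days. For p = 20%, the seen incidence is 1 − exp(ln(0.80) × 161/193.6) = 16.9%, or about 17%.

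**The case against.** A reader might infer that conjunctivitis after Week 24 is not captured at all. The documents do not support that. Adverse events are collected throughout follow-up (Sections 7.6 and 7.9.4). Section 10.5 includes events that come from an open question, observation or examination, and Table 2 schedules examinations at FU2, FU4, FU6 and early withdrawal. The treatment-emergent adverse event tables in SAP 4.8.2 also have no end date, so a diagnosed case in follow-up would appear there with its CTCAE grade. What is lost is the solicited question and the 0-3 grade. This part of the objection stands and limits the point to one table.

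A reader might also take Section 7.6 as the governing rule and the tables as departing from it. It is better read as the outlier. Table 1 footnote 11 and Table 2 footnote 4 both define efficacy assessments without conjunctivitis. The synopsis lists it under safety. Section 7.9.4, footnote 11 and both tables agree on collection in the treatment period. The wording of Section 7.6 is loose and needs reconciling, but it does not prove that collection in follow-up was intended.

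Two further inferences go too far. The last dosing interval is the first 2 of the 12 follow-up weeks, so it adds nothing to the gap. Nothing shows that early stoppers leave because of eye symptoms, and a case that did lead to stopping would be reported among adverse events leading to withdrawal.

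The objection does not supply an end of window for SAP 4.8.9 or a place in its table for a case without a 0-3 score.

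**Conclusion.** The point holds as a minor one. SAP 4.8.9 describes an open-ended window, but the graded data that feed it stop at the last treatment visit. For a completer, 34% of the time to FU6 has no solicited assessment. An early stopper is not asked again; this assumes that such patients follow Table 2, which is how SAP 4.1.4 treats efficacy visits.

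The numerical effect is uncertain. It rests on assumed incidences of 5% to 20% and an assumed hazard shape. Under a constant hazard it amounts to roughly 0.3 to 1.5 patients among 20 to 24, and fewer if the hazard falls with drug level. Those patients would be absent from the 4.8.9 table but could still be found in the adverse-event tables. The endpoint is exploratory, the study is descriptive and single-arm, and the primary endpoint is unaffected.

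**What to change.** **Protocol.** Add the conjunctivitis question and 0-3 grade to Table 2 at FU1-FU6 and at early withdrawal. Change Table 1 footnote 11, Section 7.9.4 and Section 7.6 so that all state the same schedule.

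**SAP 4.8.9.**
- State that the window runs from first dose to the last follow-up visit.
- Count a patient as a case if either the assessment or a conjunctivitis adverse event records it.
- Show patients known only from an adverse event in a separate row by CTCAE grade. Do not convert that grade to the 0-3 scale.

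**Patients already past follow-up.** Use the adverse-event record, and footnote the table to say that solicited grading ended at the last treatment visit.

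**Cost.** One question and one grade at visits that patients already attend for EASI and IGA, a repeat of one CRF page, a little data entry, and a few lines of text. The reported incidence may rise slightly.
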